8.4.2 Secondary Outcome Analyses

The secondary outcome measures include a comparison of proportions between the RTE-FNAC and US-FNAC arms. These include:

- the non-diagnostic cytology (Thy 1) rate for any FNAC undertaken in each patient;
- the number of patients out of all randomised who have surgery but have a benign histology;
- the number of FNACs required to obtain a definitive diagnosis;
- the number of patients who had a benign (Thy 2) result following first FNAC and how this compares with subsequent FNAC results in accuracy;

- the number of patients who had a benign (U2) result on US scan and how this compares with subsequent FNAC results in accuracy
- and the complication rate following any thyroidectomy out of those who had surgery.

These will all be compared between the arms using a generalised linear mixed model and adjusting for the minimisation variables. A chi-squared or Fisher's exact text (as appropriate) will be performed as secondary analyses.

The number of overall FNACs required to reach a definitive diagnosis will be compared between the RTE and US arm using a chi-squared test for trend.

Time to diagnosis will be compared between arms using a log-rank test.

Sensitivities and specificities can be calculated following US-only and RTE-only guided protocols and US-guided FNAC and presented along with 95% confidence intervals using binomial exact methods. Comparisons will be made within each arm between the tests using McNemar's test. Continuous measurements taken over time (e.g. HADS) will be analysed using .

A more detailed description of all analyses can be found in the ElaTION Statistical Analysis Plan.

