1.4. Importance of the ELaTION Trial

This study is important because of the following factors:

i. A significant health need:

Thyroid nodules affect a large proportion of the population, and are increasingly being identified incidentally on routine imaging of the head and neck. There is a need to improve the performance of US-FNAC and hence reduce the number of FNACs and diagnostic operations needed to establish a diagnosis. This may reduce the morbidity associated with the procedures (e.g. permanent loss of voice, difficulty swallowing, permanent hypocalcaemia requiring life-long medication), and decrease the inconvenience and anxiety shown to be associated with uncertainty before diagnosis, especially on repeated tests⁽⁹⁾.

ii. Considerable potential resource and cost requirements:

Thyroid nodules are very common, affecting up to 50% of population and are increasingly being detected due to increasing use of imaging technology. This could result in a significant financial burden to the NHS⁽⁵⁾.

Decreasing the number of non-diagnostic FNAC and of operations undertaken could result in considerable NHS savings.

iii. Outstanding issues in FNAC.

There remain some important questions regarding the use of ultrasound alone for diagnosis and the need for repetition of US-only guided FNAC, which have, to date, not been addressed in a large prospective randomised setting and lack level 1 evidence.

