2.2. Objectives

Primary objective:

[figure not shown]
The primary objective is to determine if RTE in conjunction with ultrasound to guide FNAC will reduce the number of patients who have a non-diagnostic (Thy 1) FNAC result following the first FNAC assessment as compared to conventional ultrasound-only guided FNAC.

Secondary objectives:

The secondary objectives are to evaluate:

- 1. Whether RTE compared to US reduces the total number of FNACs required to reach a definitive diagnosis;
- 2. Whether RTE compared to US reduces the time from first FNAC assessment until definitive diagnosis;
- 3. Whether RTE compared to US reduces the false positive rate i.e. the number of patients who receive a benign histology following surgery;
- 4. Whether RTE compared to US reduces the non-diagnostic (Thy 1) rate following all FNAC;
- 5. WhetherRTE compared to US reduces the number of patients having thyroidectomy;
- 6. Whether ultrasound alone is an accurate diagnostic modality for malignant thyroid nodules;
- 7. Whether RTE and US without FNAC is as accurate as RTE or US with FNAC;
- 8. Whether patients' anxiety, quality of life and patient reported procedural pain are improved using RTE-FNAC compared to US-FNAC;
- 9. The value of RTE in radiologist decision making and undertaking of FNAC;
- 10. Complication rates of thyroidectomy;
- 11. Whether RTE-FNAC is cost effective compared to current practice of US-FNAC.

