7.1. Follow-up assessments

Follow-up will be undertaken for 1 year from randomisation or until definitive diagnosis has been obtained if not achieved during that first year. This will be sufficient time to allow for further FNACs if required after the first test. Also this allows sufficient time for any surgery to be undertaken and histological diagnosis to be available.

For both intervention and control arms, diagnosis and management will proceed as follows:

Thy1 - repeat FNAC, especially if suspicion of malignancy. If Thy1 on three FNACs, then the recommendation is made for diagnostic surgery.

Thy 2 - repeat FNAC within 3-6 months. If two benign (Thy2) FNAC results are obtained then patient can be discharged. Consideration for discharge with a U2 scan and one Thy2 is allowed, but is not recommended for the purposes of this study.

Thy 3a - repeat FNAC within 3-6 months or discussion with MDT. Surgery may then be advised

Thy3/3f/4/5 - surgery is necessary.

All repeat FNAC must be undertaken using the same ultrasound technique as the first one specified by the randomisation and ideally by the same RTE-accredited radiologist.

All follow-up data will be captured on the relevant CRF and returned to the ElaTION Trial Office.

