7.3. Complication rates

Complication rates following thyroid operations will be recorded at 30 days and 6 months postsurgery.

Data will be collected on haematoma rate and temporary hypocalcaemia rate at 30 days and vocal cord palsy and permanent hypocalcaemia at 6 months post-surgery only.

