7.7. Definition of the End of Trial

The end of the trial will be 6 months after the last data capture, i.e. 6 months after the date of the last visit of the last patient undergoing protocol based treatment. Within ElaTION, the last visit is once the last participant has reached 1 year follow-up.

However, patients will be asked for permission to monitor long-term survival and recurrence rates through medical interventions, HES, ONS, cancer and other registry data and GP information.

The Trials Office will notify the REC the trial has ended and a summary of the clinical trial report will be provided within 12 months of the end of trial.

A copy of the end of trial notification as well as the summary report is also sent to the University of Birmingham Research Governance Team at the time these are sent to the REC.

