8.4. Statistical Analysis

A separate Statistical Analysis Plan for the ElaTION trial provides a more detailed description of the planned statistical analyses. A brief outline of the planned analyses for the primary and secondary outcome measures which are part of the main trial is given below.

The primary comparison groups will be composed of those who are in the RTE-FNAC arm to those in the US-FNAC arm. Patients, not biopsies, will be the unit of analysis. All analyses will be based on the intention to test and treat principle, with all patients analysed in the arms to which they were allocated irrespective of compliance with the randomised allocated diagnosis tool, and all patients will be included in the analyses. For all tests, summary statistics will be presented and 95% confidence intervals will be constructed where appropriate. A p-value of <0.05 will be considered statistically significant, and there will be no adjustment for multiple comparisons.

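### Thyroidectomy complications are tested between arms only among operated patients, so the test is not a randomised comparison and cannot show complications avoided by avoiding operations; the stated follow-up also conflicts with the 6-month post-operative assessment

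*Protocol*

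**What the plan says.** **Denominator.** Protocol section 8.4.2 lists the secondary outcomes to be compared as proportions. The last is "and the complication rate following any thyroidectomy out of those who had surgery". The sentence after the list reads: "These will all be compared between the arms using a generalised linear mixed model and adjusting for the minimisation variables". It is therefore a planned between-arm test, not only a descriptive safety figure.

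Other parts of the protocol bear on that choice:
- Section 2.2, objective 5: "WhetherRTE compared to US reduces the number of patients having thyroidectomy". Objective 3 seeks fewer patients with benign histology after surgery.
- Section 1.4 argues that fewer FNACs and diagnostic operations are needed, and adds: "This may reduce the morbidity associated with the procedures".
- Section 8.4 sets analysis by allocated arm, "and all patients will be included in the analyses".
- In the same list in 8.4.2, benign histology after surgery is counted out of all randomised patients.
- Section 8.1.2 (item 5) has the proportion receiving surgery, by arm, as a separate outcome.

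**Timing.** Section 7.1: "Follow-up will be undertaken for 1 year from randomisation or until definitive diagnosis has been obtained", the second limb applying only if there is no definitive diagnosis in the first year. Section 7.7: "Within ElaTION, the last visit is once the last participant has reached 1 year follow-up". Section 7.3: "Complication rates following thyroid operations will be recorded at 30 days and 6 months postsurgery". The schedule in 7.4 and item 10 of 8.1.2 repeat the 6-month post-operative assessment, which carries vocal cord palsy and permanent hypocalcaemia.

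**The concern.** Surgery follows from the cytology results, which RTE is meant to change. If RTE works as hoped, the operated patients in the two arms are differently selected. Adjusting for radiologist, nodule number, size and type cannot restore the randomised comparison, because the selection happens after those variables are measured.

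The benefit described in section 1.4 is morbidity spared in patients who no longer need an operation. Those patients leave both numerator and denominator of an operated-only rate, so the rate cannot register that benefit. At stake is the interpretation of one secondary safety result.

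The second issue is separate: the stated end of follow-up does not cover an assessment that the protocol requires for patients operated on late.

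**Working it through.** **The plan's own figures.** The protocol gives no expected rate or sample size for complications. Its primary-outcome sample size reproduces. For 10% v 4%, two-sided 5% and 90% power, the two-proportion formula gives 378 per arm, or 411 with the continuity correction. Then 411 / 0.85 = 483.5, so 484 per arm and 968 in total. The 484 is used below.

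**Inputs from the protocol**
- Cytology mix (1.2): Thy 3 5%, Thy 4 3%, Thy 5 2%, together 10%.
- Malignancy (1.3.1): Thy 3 about 20%, Thy 4 about 80%, Thy 5 98-99% (98.5% used).

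**Assumptions, not in the protocol**
- Each Thy 3-5 result leads to one operation, and the mix per FNAC is applied per patient.
- RTE halves the benign operations and leaves the malignant ones unchanged.
- Complication risks per operation are as shown in the table.
- Surgery after three Thy 1 results is left out. If repeats are independent it adds little: 484 x 0.10³ = 0.5 patients per arm, or 484 x 0.20³ = 3.9 at the audit's 20%.

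**Operations per arm**
- Total: 484 x 0.10 = 48.4.
- Malignant: 484 x (0.05 x 0.20 + 0.03 x 0.80 + 0.02 x 0.985) = 484 x 0.0537 = 26.0.
- Benign: 48.4 - 26.0 = 22.4.
- With RTE: 26.0 + 22.4 / 2 = 37.2.

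**Complications** = benign operations x benign risk + malignant operations x malignant risk. This is divided by operations, or by 484.

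| Assumed risk, benign / malignant | Complications, US to RTE | Per operated | Per randomised |
|---|---|---|---|
| 10% / 10% | 4.84 to 3.72 | 10.0% to 10.0% | 1.00% to 0.77% |
| 10% / 20% | 7.44 to 6.32 | 15.4% to 17.0% | 1.54% to 1.31% |
| 10% / 30% | 10.04 to 8.92 | 20.7% to 24.0% | 2.07% to 1.84% |
| 5% / 30% | 8.92 to 8.36 | 18.4% to 22.5% | 1.84% to 1.73% |

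In the first row complications fall by 1.12 / 4.84 = 23% and the operated-only rate does not move. In the other rows it rises while the per-randomised rate falls. If RTE avoids 25% or 75% of benign operations instead of half, the 10% / 30% row ends at 22.1% or 26.5% per operated and 1.96% or 1.73% per randomised. If the avoided operations carried higher risk than the rest, the operated-only rate would fall.

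**Timing.** For surgery in month s after randomisation, the later assessment falls in month s + 6. Surgery at month 6 gives month 12, just inside follow-up. Surgery at month 8 gives month 14, and at month 12 gives month 18, both outside. The extension in 7.1 does not help, because it runs only to definitive diagnosis and under 8.1 the histology supplies that. Surgery after month 6 is plausible on the protocol's own pathway: 7.1 allows 3-6 months for a repeat FNAC after Thy 2 or Thy 3a.

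**The case against.** **A complication rate for an operation is naturally expressed per operation.** Objective 10 names complication rates of thyroidectomy without asking whether RTE lowers them, and the morbidity remark in 1.4 is background. The general rule in 8.4 can also be read as giving way to a denominator named for one outcome. This stands as a defence of reporting the per-operated rate. It does not defend that rate as the only between-arm test.

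**Fewer operations would not go unseen.** Surgery proportion and benign histology are both compared by arm. Complications per randomised patient equal the surgery proportion times the per-operated rate, and both factors are planned. This also stands. A reader might infer that the trial would miss a fall in operations; it would not. What is missing is a planned comparison of the product, which is the randomised one.

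**Reversal is not established.** A reader might infer that RTE would come out looking harmful. The protocol gives no complication rates, so reversal rests on the assumption that the avoided operations are the safer ones. With about 4 to 10 events per arm, neither denominator would give a precise answer.

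**The 6-month form is expressly scheduled, and the trial stays open.** Section 7.7 ends the trial 6 months after the last visit, which is month 18 for the last participant. Loss of the late assessments is therefore possible but not shown. However, 7.7 places those 6 months after the last data capture, so the sections still disagree.

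**Missing 6-month data need not differ by arm.** A reader might infer that late surgery follows an initial Thy 1, and so is commoner in the control arm. Section 7.1 gives no interval for repeating a Thy 1, and nothing in the protocol ties late surgery to Thy 1 or to arm. That inference should not be made.

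**Conclusion.** The point holds in a limited form. The operated-only test in 8.4.2 compares groups selected after randomisation by something RTE is intended to reduce. It cannot show complications avoided by avoiding operations, and it sits awkwardly beside the all-patients rule in 8.4 and the all-randomised denominator used for benign histology. The protocol fixes this denominator itself, so it is not a detail left to the SAP.

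On the protocol's cytology mix, with benign operations halved and equal 10% risk (both assumed), a 23% fall in complications leaves the tested rate unchanged. That blindness needs no difference in risk between operations; reversal does. The consequence is confined to one sparse secondary outcome. The primary result and sample size are untouched.

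The timing issue is a contradiction between sections for any surgery after month 6, not evidence that data will be lost.

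**What to change.** In 8.4.2, make the between-arm comparison the number of patients with at least one thyroidectomy complication out of all randomised, counting patients who had no operation as having none. Report per-operated rates by arm descriptively, beside the surgery proportion. Patients whose surgical status is unknown should be treated as missing, not as free of complications.

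Reconcile 7.1 and 7.7 with 7.3, 7.4 and 8.1.2, so that one statement says whether data capture extends to the 6-month post-operative form for operations after month 6. The 12-month post-operative blood sample in 7.4 has the same conflict and can be settled at the same time.

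The cost is mainly wording. The per-randomised rate is smaller in absolute terms (1.00% instead of 10.0% in the equal-risk illustration). If data capture is extended, it runs some months longer for the late operations.

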11.6. Confidentiality of Personal Data	
11.7. Publication	
REFERENCE LIST	27

ELATION TRIAL SUMMARY

Trial design: Pragmatic randomised controlled trial with 1:1 randomisation.

Objectives: The primary objective is to determine if real time elastography (RTE) in conjunction with fine needle aspiration cytology (FNAC) will reduce the number of patients who have a non-diagnostic **first** FNAC result as compared to conventional ultrasound (US) only guided FNAC.

Outcome measures

Primary outcome measure

The proportion of patients who have a non-diagnostic (Thy1) cytology result following the first FNAC.

Secondary Outcome measures

- 1. Number of FNACs required to obtain a definitive diagnosis¹;
- 2. Time from first FNAC to obtaining a definitive diagnosis;
- 3. The proportion of patients with benign histology results following thyroidectomy;
- 4. Proportion of patients who have thyroidectomy;
- 5. Accuracy of a cytology result for first FNAC and repeated FNAC in relation to overall definitive diagnosis;
- 6. Accuracy of an imaging assessment on ultrasound (with or without RTE) alone diagnostic protocol in relation to overall definitive diagnosis;
- 7. Patient reported outcome measures of depression and anxiety, pain, and quality of life: the Hospital Anxiety and Depression rating Scale (HADS), Visual Analogue Pain Score (VAPS) and EQ-5D quality of life score;
- 8. Radiologist report of whether RTE had contributed to the radiologist's decisions, how easy they found using RTE, and whether they found it helpful above using US-alone in predicting malignancy;
- 9. Complication rate from any thyroidectomy at 30-days and 6-months post-surgery to include haematoma rate and temporary hypocalcaemia rate at 30 days and vocal cord palsy and permanent hypocalcaemia at 6 months post-operative;

¹ Definitive diagnosis is defined as: obtaining two benign (Thy 2) FNAC results; obtaining a single benign (Thy 2) result with a U2 benign ultrasound; obtaining histopathological diagnosis following a Thy 3, Thy 4, or Thy5 result; or obtaining histopathological diagnosis following persistently non-diagnostic (Thy 1) FNAC results

10. Resource usage for consultation time and diagnostic testing procedures and subsequent

management including consultations and surgical treatments.

Eligibility criteria

Inclusion criteria

1. Patients with single or multiple thyroid nodules whether solid or partially cystic (ie: mixed),

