4. RANDOMISATION

4.1. Randomisation method and stratification variables

Patients will be randomised into the ElaTION trial in a 1:1 ratio between RTE-guided FNAC and conventional US-guided FNAC.

A 'minimisation' procedure using a computer-based algorithm will be used to avoid chance imbalances in important stratification variables.

The stratification variables will be:

- 1. Radiologist: as ultrasound and RTE scans are operator dependent.
- 2. Solitary nodule versus multi-nodular: as multiple nodules can affect the utility and accuracy of RTE.
- 3. Size of nodule (≤4cm vs >4cm).
- 4. Solid versus mixed solid and cystic nodules. Completely cystic nodules or recent haemorrhage within a cystic nodule with no solid area are excluded: RTE and FNAC cannot be used in a completely cystic lesion.

A random factor will be incorporated into the randomisation to reduce predictability and thus avoid selection bias. This means that each patient will have a probability (unspecified here) of either being minimised, or of receiving the opposite intervention to the one they would have received if they had been minimised.

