8.1.2 Secondary Outcome Measures

The secondary outcome measures for the study are:

- 1. Number of FNACs needed to obtain a definitive diagnosis in each patient;
- 2. Time from first FNAC to obtaining a definitive diagnosis in each arm;
- 3. The proportion of patients with a benign histology, compared between arms;
- 4. The proportion of patients who have a non-diagnostic (Thy 1) cytology result following any FNAC by arm;
- 5. The proportion of patients who receive surgery by arm;
- 6. Accuracy of 1st FNAC results and repeated FNAC results, compared between arms;
- 7. If RTE or US without FNAC is as accurate as RTE or US with FNAC, compared between arms;
- 8. Patient reported anxiety, pain and quality of life(by the HADS questionnaire, VAPS and EQ-5D) at baseline and at 3, 6 and 12 months post-randomisation;
- 9. Radiologist survey-completed by radiologists at the end of the procedure to identify whether radiologists found RTE had contributed to their decisions, ease of use, and their prediction of malignancy of the nodule using RTE or US features alone;
- 10. Complication rate from any thyroidectomy at 30-days and 6 months post-surgery haematoma rate and temporary hypocalcaemia at 30 days and vocal cord palsy and permanent hypocalcaemia rate at 6 months.
- 11. Resource usage for consultation time and diagnostic testing procedures and subsequent management including consultations and surgical treatments.

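### Section 8.4.2 gives the number of FNACs to diagnosis two analyses without saying which is main, and tests time to diagnosis only by a log-rank test that ignores the minimisation factors

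*Protocol*

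**What the plan says.** Section 8.4.2 opens with a list described as comparisons of proportions. One entry is "the number of FNACs required to obtain a definitive diagnosis". Of the whole list it says: "These will all be compared between the arms using a generalised linear mixed model and adjusting for the minimisation variables". Chi-squared or Fisher's exact tests follow as secondary analyses.

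The next paragraph returns to the same outcome and states that it "will be compared between the RTE and US arm using a chi-squared test for trend". The sentence after that reads "Time to diagnosis will be compared between arms using a log-rank test". It names no strata, covariates or effect measure. Section 8.1.2 defines this outcome as "Time from first FNAC to obtaining a definitive diagnosis in each arm".

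Three other places bear on the point:

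- Section 4.1 minimises on four factors: radiologist, solitary versus multi-nodular, nodule size (4 cm cut) and solid versus mixed. The reason given for the first is "Radiologist: as ultrasound and RTE scans are operator dependent".
- Section 8.4.1 analyses the primary outcome by a mixed model with the three nodule factors as fixed effects and radiologist as a random effect. The unadjusted test is secondary.
- Section 8.4 calls any p-value below 0.05 significant, with no multiplicity adjustment.

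**The concern.** There are two faults.

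First, one outcome has two competing analyses. The adjusted model, as worded, is for a proportion, and the text does not say which proportion a count would be turned into. The trend test does suit an ordered count, but it is unadjusted. Neither is called main or supportive. With a 0.05 threshold and no multiplicity rule, an analyst who has seen the results could lead with either.

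Second, time to diagnosis departs from the protocol's own pattern. The primary outcome and the listed secondary outcomes are adjusted for the factors used in allocation, but this one is not, and no reason is given. When allocation is balanced on prognostic factors, a test that ignores them still counts their variation as noise. Its standard error is then too large, its true error rate falls below 5% and power is lost. A trend test or a log-rank test also gives only a p-value, while section 8.4 promises confidence intervals where appropriate.

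**Working it through.** **1. The plan's own figure.** The only sample size calculation is for the primary outcome (section 8.2: 10% versus 4%, over 90% power, 5% level, continuity correction).

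- Without the correction: n = [1.96·√(2·0.07·0.93) + 1.2816·√(0.10·0.90 + 0.04·0.96)]² / 0.06² = 378 per arm.
- With it: (378/4)·[1 + √(1 + 4/(378·0.06))]² = 411 per arm, or 822 in total.
- With 15% dropout: 411/0.85 = 483.5, rounded up to 484 per arm, or 968.

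All the stated figures reproduce with a two-sided test. Neither outcome discussed here has a sizing of its own, so nothing below changes 968.

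**2. The statements side by side.**

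| Outcome | Adjusted for minimisation factors | Unadjusted | Which is main? |
|---|---|---|---|
| Primary (first-FNAC Thy1) | Mixed model | Chi-squared/Fisher | Adjusted, stated |
| Other listed proportions | Mixed model | Chi-squared/Fisher | Adjusted, stated |
| Number of FNACs | Mixed model for a proportion | Chi-squared/Fisher, and trend test | Mixed model or trend test: not stated |
| Time to diagnosis | None | Log-rank | Log-rank only |

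**3. Direction of the effect.** As a linear approximation, if the balanced factors explain a share R² of outcome variance, the true two-sided error of the unadjusted test is 2·[1 − Φ(1.96/√(1 − R²))]. An assumed R² of 0.05 gives 4.4%, and 0.15 gives 3.4%. Both are below 5%.

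**4. Size, on assumed inputs.** The protocol gives no between-radiologist variation, so this simulation is only an illustration.

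- Setting: 822 patients, 30 radiologists, 2,000 runs per cell, and exact balance within radiologist by nodule type in place of minimisation.
- Prognostic effects: radiologist SD of 0.3, 0.5 or 0.8 on the log scale, and a nodule-type effect of 0.5.
- Treatment effect: 0.35 on the log-odds scale for a count of 1 to 3 FNACs, and 0.2 on the log-hazard scale for time, with censoring at 12 months.
- Comparators: a linear comparison within strata for the trend test, and a stratified log-rank for the plain log-rank.

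Type I error:

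| Radiologist SD | Trend | Adjusted | Plain log-rank | Stratified log-rank |
|---|---|---|---|---|
| 0.3 | 4.4% | 4.9% | 4.2% | 5.0% |
| 0.5 | 4.4% | 5.2% | 3.6% | 5.2% |
| 0.8 | 3.8% | 5.0% | 1.9% | 4.2% |

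Power:

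| Radiologist SD | Trend | Adjusted | Loss (points) | Plain log-rank | Stratified log-rank | Loss (points) |
|---|---|---|---|---|---|---|
| 0.3 | 72.3% | 73.8% | 1.5 | 67.8% | 71.2% | 3.4 |
| 0.5 | 70.9% | 73.4% | 2.5 | 61.4% | 68.1% | 6.7 |
| 0.8 | 66.8% | 72.8% | 6.0 | 47.0% | 67.2% | 20.2 |

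The simulation error of one entry is √(0.05·0.95/2000) = 0.5 points for type I error and about √(0.7·0.3/2000) = 1.0 point for power. The smallest differences should therefore not be over-read. The pattern is that the loss grows with radiologist variation and is larger for the log-rank.

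**The case against.** The strongest defence is that this is thin-protocol wording that the SAP will settle. The trend test can be read as the ordered-outcome counterpart of the secondary chi-squared tests, which would leave the adjusted model as main. An unadjusted log-rank is valid and widely used. The power loss concerns secondary outcomes that did not drive the sample size, and its size rests on assumed inputs. Much of this stands, and it is why the point is minor. It does not remove the point. Section 8.4.2 itself states two analyses without ranking them, and names an unadjusted test where the rest of the plan adjusts.

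A reader might infer more than the documents support:

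- *That the number of FNACs is analysed only without the minimisation factors.* It is not: the same section also gives it an adjusted model. Only the trend test is unadjusted.
- *That time to diagnosis loses patients who are never diagnosed.* A log-rank test keeps them at risk as censored observations. Section 7.1 also extends follow-up beyond one year until diagnosis.
- *That undiagnosed patients are dropped from the count.* No such exclusion is stated, and section 8.4 says that everyone is included. How unresolved patients are coded can be left to the SAP.
- *That the planned Thy1 rates show a differential loss.* They give 484 × 0.10 = 48 versus 484 × 0.04 = 19 patients with a Thy1 first result, which is not a count of patients without a diagnosis. Under section 8.1 a single Thy2 without a U2 scan is not definitive either, so unresolved patients need not be mainly Thy1.
- *That starting the clock at first FNAC loses randomised patients.* Under sections 3.2 and 4.2 randomisation normally takes place at the FNAC appointment, so any such loss should be negligible.

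**Conclusion.** The point holds as a low-severity one. Section 8.4.2 contradicts itself on the main analysis of the number of FNACs, and its adjusted entry treats a count as a proportion. Time to diagnosis has only an unadjusted test, out of line with the allocation method and with the other analyses. The consequence is conservatism and lost power, not false positives from the tests themselves: about 2 to 6 points for the trend test and 3 to 20 for the log-rank on the assumed inputs.

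Those sizes depend on how strongly radiologist and nodule factors predict the outcome, which the protocol does not report. If the factors are weak predictors, the loss is small. The upper end needs marked radiologist variation (SD 0.8). The contradiction over the number of FNACs depends on no assumption.

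**What to change.** In section 8.4.2, and in step with the SAP, name one main analysis for each outcome.

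- **Number of FNACs:** remove it from the list of proportions. Use an ordinal (or count) mixed model with nodule number, size and solid/mixed type as fixed effects and radiologist as a random effect. Label the chi-squared trend test supportive.
- **Time to definitive diagnosis:** use a Cox model adjusted for the same three nodule factors, with radiologist as frailty or stratum, and report the hazard ratio with its 95% confidence interval. A stratified log-rank is an acceptable alternative for the test. State that undiagnosed patients are censored at last contact. Label the plain log-rank supportive.

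This matches how section 8.4.1 already ranks adjusted and unadjusted analyses. Every covariate is recorded at randomisation, so there is no new data collection and no change to the sample size. The cost is a few sentences of wording, best settled before anyone sees outcome data by arm.

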8.2. Sample size

We plan to recruit a sample of 968 patients to achieve over 90% power for detecting the following difference in the primary outcome at the 5% significance level, allowing for 15% loss to follow-up.

An audit of US- only guided FNACs in one institution, suggested that Thy1s made up 20% of FNAC results ⁽⁶⁾. This is likely to be an overestimate as this was including cystic nodules, so a more conservative estimate of 10% is assumed in calculating the sample size. The hypothesis is that using RTE in addition to US in guiding the FNAC would reduce the number of Thy1s to 4%. To detect this difference, with a continuity correction, requires 411 patients in each arm or 822 in total. Therefore, after adjusting for 15% drop-out rate, a total of 968 patients is required.

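### McNemar's within-arm difference test cannot show that imaging without FNAC is as accurate as imaging with it, and on sensitivity a non-significant result would say little

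*Protocol*

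**What the plan says.** Objective 7 in Protocol section 2.2 is "Whether RTE and US without FNAC is as accurate as RTE or US with FNAC". Section 8.1.2 carries it forward as outcome 7: "If RTE or US without FNAC is as accurate as RTE or US with FNAC, compared between arms". Outcome 6 in the same list is "Accuracy of 1st FNAC results and repeated FNAC results, compared between arms".

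Section 8.4.2 says that sensitivities and specificities can be calculated for the imaging-only and FNAC protocols and presented with exact binomial 95% CIs. It then says: "Comparisons will be made within each arm between the tests using" McNemar's test. Section 8.4 sets the significance rule at p<0.05 without multiplicity adjustment.

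Section 8.4.2 also lists two items described as accuracy: a first Thy2 result against later FNAC, and a U2 scan against later FNAC. These belong to a group to be compared between arms by a generalised linear mixed model, with chi-squared or Fisher's exact test as secondary. No equivalence or non-inferiority margin appears anywhere in the protocol.

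**The concern.** The question and the named test point in different directions. Asking whether one strategy is as accurate as another is an equivalence or non-inferiority question. McNemar's null hypothesis is no difference. Rejecting it shows that accuracy differs; not rejecting it leaves the question open. No outcome of the test supports a yes to objective 7.

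This matters most for sensitivity, because missed cancers are the cost of relying on imaging alone, and the number of cancers is small. Section 1.6 names the efficacy of ultrasound-only protocols among the main open questions that the trial will try to answer, so this result is likely to be used.

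A second mismatch concerns the contrast. Outcomes 6 and 7 are declared as compared between arms, but the only test named for sensitivity and specificity is within arm.

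**Working it through.** **The plan's own figure.** Section 8.2 uses Thy1 rates of 10% and 4%, 5% significance and 90% power. The two-sided two-proportion formula gives 377.9 per arm without continuity correction. With it, n = (377.9/4) × [1 + √(1 + 4/(377.9 × 0.06))]² = 410.6, so 411. This agrees with "with a continuity correction, requires 411 patients in each arm or 822 in total". Then 822/0.85 = 967.1, which is 968 for equal arms, or 484 per arm. The size was set for the primary outcome; no figure is given for accuracy.

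**Cancers per arm** (prevalence from section 1.1):
- As randomised: 484 × 0.04 = 19.4 and 484 × 0.07 = 33.9.
- After 15% loss: 411 × 0.04 = 16.4 and 411 × 0.07 = 28.8.
- Cross-check from the audit mix (section 1.2) and malignancy by category (section 1.3.1, taking 98.5% for Thy5): 0.05 × 0.20 + 0.03 × 0.80 + 0.02 × 0.985 = 5.4%, or 26 per 484. This leaves out cancers behind Thy1 and Thy2 results.

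**McNemar power on sensitivity.** The protocol gives no discordance rates, so these are assumptions. Let p10 be the share of cancers detected only with FNAC and p01 the share detected only without it; the true loss is p10 − p01. Power is the sum, over the number m of discordant pairs, of P(m) × P(reject | m), with m binomial (n, p10 + p01) and the split of m binomial (m, p10/(p10 + p01)). Each cell shows the exact two-sided test / uncorrected chi-squared test.

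| Cancers | 15-point loss (20% v 5%) | 15-point loss (15% v 0%) | 20-point loss (25% v 5%) |
|---|---|---|---|
| 16 | 5% / 21% | 2% / 21% | 11% / 31% |
| 20 | 10% / 26% | 7% / 35% | 20% / 38% |
| 26 | 18% / 33% | 19% / 56% | 33% / 47% |
| 34 | 29% / 41% | 40% / 77% | 47% / 58% |

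**Precision.** For a paired difference near zero with total discordance d, the approximate 95% half-width is 1.96 × √(d/n). At d = 10-20% this is 14-20 points with 20 cancers and 11-15 points with 34.

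**What a margin would need (illustration only; margin and discordance assumed).** With no true difference, n = d × (1.96 + 0.84)²/margin². At one-sided 2.5% and 80% power, a 10-point margin needs 79 cancers at d = 10% or 157 at d = 20%. A 15-point margin needs 35 or 70. For the 10-point margin, 20 cancers give 17-29% power and 34 give 26-45%.

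**Specificity.** At 7% malignancy, 484 × 0.93 = 450 benign patients per arm. Uncorrected chi-squared McNemar power is 79% for a 5-point difference (10% v 5% discordant) and over 99% for 10 points (15% v 5%). For 5 points with more discordance (15% v 10%) it is 57%.

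**The case against.** The protocol never says that a non-significant McNemar result means equal accuracy. A reader might infer that it would be taken that way, but section 8.4.2 also plans an exact 95% CI for each test, and those would expose the imprecision: 24 detected of 26 has an exact interval of 75-99%. The Trial Summary words the imaging outcome descriptively, as accuracy against the definitive diagnosis, and sensitivity and specificity with CIs answer that version. McNemar's test is the standard difference test for two tests in the same patients. All of this stands. Even so, two separate intervals are not an interval for the paired difference, and sections 2.2 and 8.1.2 do ask the comparative question.

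A reader might also infer that the between-arm accuracy outcomes have no test at all. That is too broad, because the Thy2 and U2 items have a between-arm mixed model and overlap outcomes 6 and 7. The gap is confined to sensitivity and specificity themselves.

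Nor do small numbers undermine the whole accuracy comparison; specificity has several hundred patients per arm. The power figures for sensitivity depend on assumed discordance and on the form of the test, which the protocol does not specify. The most favourable 15-point case above (15% v 0%, chi-squared, 34 cancers) reaches 77%.

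Finally, a margin and an estimator are often left to the SAP, which is not available here, and their absence alone would not be a point. The point rests on what the protocol does state: a test that does not fit its objective, and a within-arm contrast for an outcome declared between arms.

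**Conclusion.** The point holds in this limited form. The named difference test cannot give a positive answer to objective 7. For sensitivity, a non-significant result would be weak evidence: with 20-34 cancers per arm and assumed discordance of 20% v 5%, a 15-point loss would be missed 71-90% of the time by the exact test and 59-74% by uncorrected chi-squared. The cancer counts follow from the protocol's prevalence and sample size; the discordance rates are assumptions. The small-number problem does not extend to specificity. The mismatch between sections 8.1.2 and 8.4.2 over the between-arm contrast is real but partial. This is a secondary objective and the primary analysis is unaffected. The change is still worth making, because it alters what may be concluded about imaging alone.

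**What to change.** For objective 7, make the within-arm paired difference in sensitivity and in specificity (imaging without FNAC minus imaging with FNAC), each with a 95% CI, the main result. Conclude that imaging alone is as accurate only if the interval excludes a loss as large as a margin chosen and stated in advance by the clinical team; otherwise report the comparison as inconclusive. Keep McNemar's test as supportive only.

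Reconcile sections 8.1.2 and 8.4.2 by adding the between-arm difference in sensitivity among patients with malignant nodules and in specificity among those with benign nodules, each with a 95% CI. The mixed model for the Thy2 and U2 items can stay.

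The cost is a wording change in the protocol and SAP and agreement on a margin, with no new patients or data. The drawback is that the sensitivity conclusion will probably be inconclusive.
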